### **13.5.1 Confidentiality**

All Individual participant medical information obtained as a result of this trial is considered confidential and disclosure to third parties is prohibited with the exceptions noted below.

Case report forms will be labelled with the participant's initials and unique trial screening and/or randomisation number. Medical information may be given to the participant's medical team and all appropriate medical personnel responsible for the participant's welfare.

The MC CTU will be undertaking activities requiring the transfer of identifiable data:

Verification that appropriate informed consent is obtained will be enabled by the provision of copies of participant's signed informed consent/assent forms being supplied to the MC CTU by recruiting sites, which requires that name data will be transferred to the MC CTU. This will also enable future follow-up of participants to occur.

This transfer of identifiable data is disclosed in the PISC. The MC CTU will preserve the confidentiality of participants taking part in the trial and The University of Liverpool is registered as a Data Controller with the Information Commissioners Office.

### **13.5.2 Quality Assurance and Control**

QA includes all the planned and systematic actions established to ensure the trial is performed and data generated, documented/recorded and reported in compliance with applicable regulatory requirements. QC includes the operational techniques and activities done within the QA system to verify that the requirements for quality of the trial-related activities are fulfilled e.g. state what clinical site monitoring (and audit) is planned, if any.

- Data will be evaluated for compliance with protocol and accuracy in relation to source documents

- The trial will be conducted in accordance with procedures identified in the protocol.
- The Principal Investigator and RN from each site will attend the trial launch meeting, coordinated by MC CTU in conjunction with the Co-Chief investigators, [name] and [name], which will incorporate elements of trial specific training necessary to fulfil the requirements of the protocol;
- The Trial Coordinator is to verify appropriate approvals are in place prior to initiation of a site and the relevant personnel have attended trial specific training;
- The Trial Coordinator is to check safety reporting rates between sites;
- The Trial Coordinator is to monitor screening, recruitment and drop-out rates between sites;
- The Trial Coordinator is to conduct data entry consistency checks and follow-up data queries;
- Independent oversight of the trial will be provided by the Data and Safety Monitoring Committee and independent members of the Trial Steering Committee.

### **13.6 Records Retention**

The investigator at each investigational site must make arrangements to store the essential trial documents, (as defined in Essential Documents for the Conduct of a Clinical Trial (ICH E6, Guideline for Good Clinical Practice)) including the Investigator Site File until the Clinical Trials Unit informs the investigator that the documents are no longer to be retained, or for a maximum period of 15 years (whichever is soonest).

In addition, the investigator is responsible for archiving of all relevant source documents so that the trial data can be compared against source data after completion of the trial (e.g. in case of inspection from authorities).

The investigator is required to ensure the continued storage of the documents, even if the investigator, for example, leaves the clinic/practice or retires before the end of required storage period. Delegation must be documented in writing.

The MC CTU undertakes to store originally completed CRFs for the same period, except for source documents pertaining to the individual investigational site, which are kept by the investigator only. The MC CTU will archive the documents in compliance with ICH GCP utilising the Records Management Service of the University of Liverpool. All electronic CRFs and trial data will be archived onto an appropriate media for long term accessible storage. Hard copies of data will be boxed and transferred to specially renovated, secure, premises where unique reference numbers are applied to enable confidentiality, tracking and retrieval.

## 14 INDEMNITY

PREVAIL is sponsored by UCL-Institute of Child Health and co-ordinated by the MC CTU in the University of Liverpool. The UCL-Institute of Child Health insurance policy covers for non-negligent harm to trial participants, that is, compensation to participants where negligence cannot be, or is not, proved.

However, in terms of liability, NHS Trust and Non-Trust Hospitals have a duty of care to patients treated, whether or not the patient is taking part in a clinical trial, and they are legally liable for the negligent acts and omission of their employees.

**Clinical negligence is defined as:**

“A breach of duty of care by members of the health care professions employed by NHS bodies or by others consequent on decisions or judgments made by members of those professions acting in their professional capacity in the course of their employment, and which are admitted as negligent by the employer or are determined as such through the legal process”.

## **15 FINANCIAL ARRANGEMENTS**

This trial is funded by the Health Technology Assessment programme (HTA) of the Department of Health. Contractual agreements will be in place between sponsor and collaborating sites that will incorporate financial arrangements.

Trial participants will not be paid to participate in the trial. The schedule of the trial will be in line with routine standard care.

As the trial is funded by the NIHR HTA, it will automatically be adopted onto the NIHR portfolio, which will allow trusts to apply to their comprehensive local research network for service support costs if required.

### **15.1 Financial Support to Collaborating Sites**

#### **15.1.1 Staffing**

0.33 FTE RNs will be employed at each of the confirmed participating trial sites to support the identification, recruitment and management of participants for the PREVAIL trial.

#### **15.1.2 PICCs supplied by Vygon**

The devices S-PICC and AM-PICC will be supplied by Vygon to the recruiting sites for use in the trial as per the following pricing structure, for the duration of the individual recruiting sites participation in PREVAIL.

The Trial Coordinator will be responsible for informing Vygon of a Recruiting sites participation and closure to PREVAIL. Recruiting sites will only be able to source the PICCs at the discounted price once all required approvals are in place and the sites have been initiated into the trial.

- S-PICCs at list price
- AM-PICCs same price as S-PICCs list price.

#### **15.1.3 Other payments**

Funding for culture and antibiotic resistance testing

## **16 TRIAL COMMITTEES**

### **16.1 Trial Management Group (TMG)**

A Trial Management Group (TMG) will be formed comprising the Co-Chief Investigators, other lead investigators (clinical and non-clinical) and members of the MCRN Clinical Trials Unit. The TMG will be responsible for the day-to-day running and management of the trial and will meet approximately 3 times a year. Refer to the TMG terms of reference and trial oversight committee membership document for further details.

### **16.2 Trial Steering Committee (TSC)**

The Trial Steering Committee will consist of an independent chairperson, an independent expert in the field of neonatology, a biostatistician and a lay member. The role of the TSC is to provide overall supervision for the trial and provide advice through its independent Chairman. The ultimate decision for the continuation of the trial lies with the TSC. Refer to the TSC terms of reference and trial oversight committee membership document for further details.

### **16.3 Independent Data and Safety Monitoring Committee (IDSMC)**

The independent Data and Safety Monitoring Committee (IDSMC) consists of an independent chairperson, plus 2 independent members. Members include an expert in the field of microbiology and an expert in medical statistics.

The IDSMC will be responsible for reviewing and assessing recruitment, interim monitoring of safety and effectiveness, trial conduct and external data. The IDSMC will first convene prior to the start of recruitment and will then define frequency of subsequent meetings (at least annually). Details of the interim analysis and monitoring are provided in section 9.

The IDSMC will provide a recommendation to the Trial Steering Committee concerning the continuation of the trial. Refer to the IDSMC charter and trial oversight committee membership document for further details.

## PART II: ECONOMIC ANALYSES

### 17 ECONOMIC ANALYSES

The economic analysis will estimate:

- a) The direct hospital costs of using AM-PICC compared with S-PICC over 6 months from randomisation.
- b) The cost-effectiveness of AM-PICC compared with S-PICC over the participants' expected lifetime from the perspective of the NHS
- c) The potential value of additional research to reduce any uncertainty observed in the cost-effectiveness model. This will be used to inform decisions about long-term follow up of the trial cohort.
- d) The value of implementing the cost-effective intervention (AM-PICC vs S-PICC) throughout the NHS in England and Wales
- e) The costs of a BSI to the NHS.

The evaluation of the hospital costs (a) of using AM-PICC compared with S-PICC over the time horizon of the trial (6-months) will use routinely collected data from the National Neonatal Research Database (NNRD), Paediatric Intensive Care Audit Network (PICANet), and Hospital Episode Statistics (HES) inpatient and outpatient and Accident and Emergency (A&E), complemented as needed with hospital administrative data, over the six months of follow-up. Hospital administrative data will be used when NNRD does not hold the complete data on the baby's admission, this is the case for several of the participating hospitals that do not contribute towards NNRD. For the remaining hospitals the NNRD will provide data on the NNU stay.

PICANet will provide data on any stay in a paediatric intensive care unit. HES inpatient, outpatient and A&E will provide data on hospitalisations, outpatient appointments and A&E attendance respectively, including transfers out of the neonatal unit during the initial admission. Parent or guardian consent will be sought to obtain data on morbidity, mortality and resource use from PICANet, HES, hospital administrative data and NNRD. Participant identifiers (NHS number, date of birth, gender, name and postcode) of the babies recruited for the trial will be used to request health and social care data from the Health & Social Care Information Centre (H&SC IC) for HES, from the Neonatal Data Analysis Unit (NDAU) for NNRD, from the PICANet administrators for PICANet, from the relevant hospital finance departments for hospital administrative data and ONS for deaths. The health economics team (at the Centre for Health Economics - University of York [CHE]), with the assistance of the chief investigator, will request the data from HES, PICANet, NNRD and ONS, which will held be at CHE.

Data on resource use is held in PICANet, HES and NNRD as Healthcare Resource Group (HRG) Version 3.5. However, NHS reference costs are provided for HRG Version 4. Therefore, the data on resource use in HES and NNRD will be converted to HRG Version 4 for costing. The relevant HRG Version 4 codes are: XA01Z for intensive care, XA02Z for high dependency care, XA03Z for special care, XA04Z for special care with primary carer resident or transitional care, XA05Z for normal care and XA06Z for transportation Hospital

administrative data will be collected as number of days in each HRG code if the hospital has such records available. Alternatively, relevant resource use data will be collected to inform the costing procedure (grouping according to the HRG). The HRG codes may be updated over time following the UK Department of Health guidance for the use of HRGs. The costs of AM-PICC and of S-PICC will be based on the purchasing costs by the participating sites.

The cost-effectiveness analysis (b) will estimate the difference in NHS costs and health outcomes over the participants' lifetime of using AM-PICC vs S-PICC. This will involve the development of a new decision-analytic model, following the principles established in the reference case by the National Institute of Health and Care Excellence (NICE) (36). The decision-analytic model will link the evidence on short term outcomes collected in the trial (BSI, necrotising enterocolitis, antibiotic exposure, sepsis, etc.) to external evidence on the risk of adverse neurodevelopmental outcomes in early childhood (e.g. cerebral palsy, vision impairment, hearing impairment, motor impairment, etc.). Studies on the relationship between different outcomes (e.g. odds ratio for cerebral palsy associated with necrotising enterocolitis) will be obtained from an informal literature review, advised by the clinical team. Adverse neurodevelopmental outcomes in early childhood will be linked to estimates of the loss of health and additional costs in early adolescence obtained from external evidence (37). Final health outcomes will be expressed as quality-adjusted life years (QALYs). The model will be probabilistic and Monte Carlo simulation will be used to propagate the uncertainty in the input parameters. Cost-effectiveness acceptability curves (CEACs) will be used to represent the probability that an intervention (AM-PICC or S-PICC) is a cost-effective use of NHS resources over a range of cost-effectiveness threshold values (38). In addition, the structure of the decision-analytic model will be informed by a systematic review of published cost-effectiveness models in interventions that reduce the risk of BSI in neonates.

The value of information analysis (c) will be conducted to assess the value of potential additional research, to identify which research is most valuable to the NHS and estimate the maximum investment that should be allocated to such research. The value of information analysis will estimate the expected value of perfect information and, if appropriate, the expected value of perfect information for parameters (39).

The value of implementation analysis (d) will estimate the value of implementing the cost-effective technology (AM-PICC or S-PICC) throughout the NHS in England and Wales. It will combine the information on the baseline risk of BSI and the number of PICC required all NHS NNUs, estimated in the Generalisability analysis (see Section 18) with the additional value of the cost-effective technology.

The evaluation of the costs of a BSI to the NHS (e) will take two stages. This first stage involves the evaluation of the costs of a BSI to the hospital over the time horizon of the trial by regressing hospital costs on and the number of BSI and other adjusting variables as appropriate. The first stage will be performed if there are differences in hospital costs and in the BSI rate between the groups allocated to AM-PICC and S-PICC. On a second stage, decision model built for b) will be used to estimate the lifetime costs of a BSI to the NHS.

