### 4.2 Secondary Endpoint(s)

Outcomes captured up until 48 hours after PICC removal:

1. Rifampicin resistance in any isolate from blood/CSF culture.
2. Rifampicin resistance in any isolate from PICC tips.
3. Type of organism isolated from BSI.
4. Rate of BSI per 1000 PICC-days (including recurrent BSI).
5. Occurrence of 1 or more BSI.
6. Rate of catheter-related BSI per 1000 PICC days.
7. Rate of blood/CSF culture sampling per 1000 PICC days.
8. Duration of antimicrobial exposure from randomisation up to 48 hours after line removal.
9. Time to PICC removal.

Outcomes captured up until discharge home from neonatal care/death/6 months post randomisation:

10. Chronic lung disease 36 weeks postmenstrual age.
11. Necrotizing enterocolitis (NEC): Bell's stage II or III.
12. Treatment for retinopathy of prematurity.
13. Abnormalities on cranial ultrasound.
14. Time to full milk feeds after randomisation.
15. Total duration of parenteral nutrition from randomisation until discharge from NNU.
16. Death:
  - a) within 6 months (26 weeks) of randomisation
  - b) before discharge home from neonatal care
  - c) Time to death

For health economics outcomes, please refer to Part II: Economic Analysis.

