## 6.5 Clinical Follow-up – starting at Randomisation

The following information will be captured on Form 4: Daily Follow-up which should be completed for each day from randomisation until 48 hours after randomised PICC removal / attempted insertion / randomisation if not attempted as per table 1 section 8.2. It may be completed retrospectively but it must be completed regularly (at a minimum of every 7 days). It should be completed as at 23.59 on the specified dates.

- Randomised PICC status (in situ/removed/etc)
- PICC tip culture taken (if applicable) – Form 5: Microbiology also needs updating
- Blood/CSF cultures samples taken – Form 5: Microbiology also needs updating
- Antibiotics/Antifungals
- Related adverse events – Form 8: Related AEs also needs updating

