### 9.4 Sample Size

When the sample size in each group is 408, with a total number of blood stream infections required of 79, a 0.050 level two-sided log-rank test for equality of survival curves will have 90% power to detect the difference between a proportion of 0.14 and a proportion of 0.07 (a constant hazard ratio of 2.078). Assuming 5% loss to follow up due to transfers, we estimate that 858 babies would need to be randomised (429 to each arm).

The basis of this calculation is as follows:

- i) Baseline event rate: The incidence of BSI in babies less than 32 weeks gestation with PICC was assumed to be 14/1000 CVC days, based on unpublished audits of BSI event rates at 3 hospitals (Table 2). Hospital A shows a recent reduction in BSI which follows a series of hospital infection control initiatives. As other units have not seen major reductions in rates, and recent rates from one unit are as high as 20/1000 CVC days, we have used 14/1000 CVC days for the sample size estimate. In addition, the rates in Table 2 are considered conservative as the denominators include a minority of babies with umbilical venous catheters and surgically inserted venous catheters for which the rate of BSI is lower than for PICC. In addition, the rates of BSI measured in the units reflects all kinds of CVC, and babies for whom Premicath insertion is appropriate may be expected to experience BSI more frequently than typical NNU inpatients.
- ii) Duration of PICC insertion. This was estimated as a median of 10 days, based on an audit of 5 NNUs (with mean duration ranging from 10 to 29 days). Hence the proportion of babies with a BSI in the standard arm is estimated to be 14%.
- iii) A 50% absolute reduction in the event rate. This is conservative when viewed against results of a network meta-analysis by Wang et al (mean odds ratio 0.18 and upper

limit of a 95% confidence interval of 0.34) because of the factors that may attenuate the treatment effect in very preterm babies (see section 2.2).

- iv) A 5% loss to follow is realistic as follow up should be complete for babies remaining on the NNU, but a very small number may be transferred with their PICC in-situ. Efforts will be made to capture primary outcome data for babies transferred to non-participating NNUs.

Table 3 demonstrates the impact on statistical power of the control group event rate variation maintaining the sample size of 408 in each group (prior to adjusting for loss to follow up).

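### Section 17(e) regresses 6-month hospital cost on the number of BSIs and ignores time at risk, so the cost of a BSI will generally be too high if longer PICC dwell goes with longer stay

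*Protocol*

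**What the plan says.** Section 2.3.2.2 lists the cost of a BSI to the NHS as the fifth secondary economic objective. Section 17(e) answers it in two stages. Stage one estimates the hospital cost within the trial "by regressing hospital costs on and the number of BSI and other adjusting variables as appropriate". It runs only if the arms differ in both hospital cost and BSI rate. Stage two uses the decision model from 17(b) to reach a lifetime figure.

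The cost horizon is set earlier in section 17, "over the time horizon of the trial (6-months" from randomisation. Cost depends heavily on days in care. At hospitals that do not contribute to the NNRD, "administrative data will be collected as number of days in each HRG code" where such records exist; "For the remaining hospitals the NNRD will provide data on the NNU stay".

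Section 4.2 heads the BSI outcomes "Outcomes captured up until 48 hours after PICC removal", and section 6.5 has the daily form completed "for each day from randomisation until 48 hours after randomised PICC removal" (or after attempted insertion or randomisation where no line was placed). The trial's own recurrent measure has an exposure denominator: "Rate of BSI per 1000 PICC-days (including recurrent BSI". Section 17(e) has none. It names no adjusting variable, does not mention when the BSI occurred, and does not say over what window BSIs are counted.

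**The concern.** The outcome is a cumulative total that includes every day before the infection. The regressor is a raw count of an event that can only accrue while the baby is at risk. A baby whose line stays in longer has more opportunity for a counted BSI. If such babies also tend to stay in hospital longer, their extra cost is credited to BSI even where the BSI added nothing. Randomisation gives no protection, because the regressor is a post-randomisation event and not the allocated arm.

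At stake is the figure reported for secondary economic objective 5. It could be clearly positive when BSI adds no stay at all, or well above the truth when BSI does add stay.

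**Working it through.** The plan states no figure for the cost of a BSI, so there is none to reproduce. The check asks how large a false effect the stage-one regression could return.

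**Inputs from the Protocol.** Section 9.4 gives 14 BSI per 1000 CVC days and "Duration of PICC insertion. This was estimated as a median of 10 days, based on an audit of 5 NNUs". These agree with each other: 0.014 × 10 = 0.14, the 14% control-arm proportion (as a probability of at least one event, 1 − exp(−0.14) = 0.131). The counting window, from 24 hours after randomisation to 48 hours after removal, is about dwell + 1 day if the line is inserted promptly. The horizon is 26 weeks = 182 days.

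**Assumptions not in the documents.** Dwell D is lognormal (median 10 days, log-SD 0.7). Stay L is lognormal (median 60 days, log-SD 0.5). Their log-scale correlation ρ runs from 0 to 0.8, and D is capped at L. Days of stay stand in for cost. The true effect of a BSI is 0 or 7 days.

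**Model.** BSI count B is Poisson with mean 0.014 × (D + 1), and stay is min(L + effect × B, 182). Ordinary least squares of stay on B was fitted to 2,000,000 simulated babies.

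**Hand check at ρ = 0.4, true effect zero, caps ignored.** With r = 0.014, the slope is Cov(L, B)/Var(B) = Cov(L, D) / [E(D) + 1 + r·Var(D)].
- E(D) = 10·exp(0.245) = 12.78; Var(D) = 12.78² × (exp(0.49) − 1) = 103
- E(L) = 60·exp(0.125) = 68.0
- Cov(L, D) = 12.78 × 68.0 × (exp(0.4 × 0.7 × 0.5) − 1) = 131
- Slope = 131 / (12.78 + 1 + 1.45) = 8.6 days, against 8.2 in the simulation with the caps.

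**Simulated days of stay credited to each BSI.**

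| ρ | truth 0, count only | truth 7, count only | truth 0, dwell added | truth 7, dwell added |
|---|---|---|---|---|
| 0 | 0.5 | 7.5 | −0.07 | 6.9 |
| 0.2 | 4.1 | 11.1 | −0.04 | 6.9 |
| 0.4 | 8.2 | 15.0 | −0.02 | 6.8 |
| 0.6 | 12.5 | 19.1 | −0.01 | 6.7 |
| 0.8 | 17.0 | 23.5 | −0.03 | 6.7 |

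**Can a covariate repair it?**
- *Total stay.* With a true effect of 7 days, adjusting for total stay returns 0, because stay is the path through which the BSI acts.
- *Observed line-days.* The last two columns look reassuring, but they assume that a BSI never ends the line. Section 5.4 lists infection among the clinical reasons for removal. If half to all lines are removed at the first BSI, and ρ is 0.4 to 0.6, the dwell-adjusted regression returns about 5 to 21 false days per BSI when the truth is zero. A short observed dwell that ended in a BSI is then compared with short dwells that were always going to be short.

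**Counting window.** If the number of BSIs were instead counted over the whole stay, at 2 to 14 per 1000 days, the false excess with a true effect of zero would be about 17 down to 14 days.

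**The case against.** The strongest defence is that section 17(e) is an outline. Adjusting variables are to be used as appropriate, nothing excludes time at risk, and a later analysis plan could name it. In the simplest simulated setting, adding line-days does recover the truth. With no dwell-stay correlation the bias is only about half a day. Stage one may never run, since it needs a difference in both cost and BSI rate. The by-arm cost comparison in 17(a) does not use this regression, and 17(b) does not name its coefficient as an input.

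The points on scope and on unknown size stand. The point on covariates does not rescue the method. The outcome (cumulative cost) and the regressor (number of BSIs) are already fixed. Of the two natural time adjustments, one removes the effect being sought and the other fails if infection ends the line.

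A reader might go further than the documents allow in four ways:
- **That a long stay in itself gives more time for a counted BSI.** BSI outcomes stop 48 hours after removal, so later stay adds cost but no exposure. The route is PICC dwell, unless 17(e) means a wider window that it does not state.
- **That the false excess is 12 days.** Regressing line-days on BSI count, with exponential dwell of mean 10/ln 2 = 14.4 days, does give Var(D)/(mean + r·Var(D)) = 208/(14.4 + 2.9) = 12.0. The plan regresses cost, and nothing in the Protocol says that each extra line-day adds one day of stay.
- **That the estimate is too high whenever dwell varies.** Dwell must also be positively associated with stay or cost.
- **That adjusting for line-days wipes out the true effect.** It does not (6.7 to 6.9 against a truth of 7). Its failing is bias when a BSI ends the line.

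**Conclusion.** The concern holds in a limited form. The stage-one method relates a cumulative cost to a count of a time-dependent event, with no handling of time at risk or timing, and it will generally overstate the cost of a BSI when dwell and stay are positively associated. That association is plausible, but the Protocol does not quantify it.

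The size cannot be derived from the documents. Under the assumed distributions it runs from about 0.5 to 17 false days of stay per BSI across correlations of 0 to 0.8, and the conversion from days to cost is a further assumption. The direction and mechanism are well supported; any single figure is not. One secondary economic objective is affected, conditional on stage one being triggered. The primary clinical analysis is not affected.

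**What to change.** In section 17(e):
1. Define the window in which BSIs are counted and say whether recurrences count.
2. Make a time-dependent analysis the main stage-one method. One choice is a multistate model (at risk, BSI, discharge or death) that gives excess days after BSI, priced by care level. Another compares cost accrued after a BSI with cost accrued after the same line-day in babies still at risk and BSI-free.
3. Adjust for gestation, birth weight and NNU. Do not adjust for total stay, and do not rely on observed line-days as the correction.
4. Keep the simple regression only as a labelled crude estimate.

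The cost is a little more analyst time. Culture sampling and line status are already recorded day by day, and care-level stay data are already requested. One detail to settle: where a hospital supplies only counts of days per care level, dates are needed to separate cost before a BSI from cost after it. The Protocol does not say whether those counts are dated.
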